- Need for alternative treatment of depressive symptoms as determined by the investigator

Upon meeting any of the relapse criteria at any visit in the DBTP, the patient will be considered a completer and the Visit 69/ET Visit procedures should be conducted.

Each randomized patient will be treated until relapse criteria are met, or until he/she has completed 52 weeks of double-blind treatment or discontinued for other reasons. The study will be terminated when all randomized patients have either met relapse criteria, early terminated for other reasons, or completed 52 weeks of the DBTP and completed the safety-follow up period where appropriate.

Upon completion of the DBTP, patients will enter a 2-week safety follow-up period.

[figure not shown]

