#### **9.7.5 Efficacy Analyses**

All efficacy analyses for the OLTP will be performed using the Open-label mITT Population. All efficacy analyses for the DBTP will be performed using the Double-blind mITT Population. The baseline of the lead-in study will be used as the baseline for the OLTP and the DBTP. All statistical tests will be 2-sided hypothesis tests performed at the 5% level of significance and all confidence intervals (CIs) will be 2-sided 95% CIs, unless stated otherwise.

An additional analysis plan specific to European Medicines Agency will be presented in a stand-alone document.

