# 2.0 INTRODUCTION

This Statistical Analysis Plan (SAP) describes the methodology that will be used to summarize the statistical analyses of the efficacy and safety data for the final protocol of Study RAP-MD-33 (version dated 02MAY2018).

Study RAP-MD-33 is a Phase 3, multicenter, randomized-withdrawal, parallel-group, placebo-controlled, maintenance study to evaluate the efficacy, safety, and tolerability of rapastinel in the prevention of relapse in patients with major depressive disorder (MDD) who completed one of the rapastinel lead-in studies including RAP-MD-30 and RAP-MD-32. The RAP-MD-31 study was terminated before any patient was enrolled. Thus, there is no patient rolled-over from the RAP-MD-31 study to RAP-MD-33 study.

The study will be conducted in the following periods:

- An 8- to 16-week open-label treatment period (OLTP) where patients receive rapastinel 225 or 450 mg IV weekly
- A randomized double-blind treatment period (DBTP) of at most 52 weeks of treatment duration where patients are randomized 1:1:1 to either rapastinel 225 or 450 mg weekly, rapastinel clinically driven schedule (IV, 225 or 450 mg, variable interval, placebo on intervening weeks) or placebo
- A 2-week safety follow-up period

In order for patients to transition from the OLTP and be randomized into the DBTP, the patient must meet the stability criterion sometime after 8 weeks (and up to 16 weeks) during the OLTP. A patient will be considered a stable responder upon achieving both criteria (1) and (2) below:

- 1) An observed Montgomery-Asberg Depression Rating Scale (MADRS) total score  $\leq 12$  with no more than one modest MADRS excursion (MADRS total score > 12 but  $\leq 16$ ) for at least six consecutive weeks.
- 2) An observed MADRS total score  $\leq 12$  for at least two consecutive visits prior to randomization.

The OLTP starts with the first dose of open-label treatment and ends with one of the following: the first dose of double-blind treatment for patients who enter the DBTP or Visit 69/Week 52 End-of-Treatment/Early Termination (ET) assessments for patients who do not enter the DBTP.

The double-blind treatment period starts when the first dose of double-blind treatment is administered and ends when the patient meets relapse criteria, completes 52 weeks of double-blind treatment, or discontinues for other reasons.

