An AE (classified by preferred term) that occurs during the SFU of the study will be considered a newly emergent adverse event (NEAE) if the AE was not present before or at Visit 70 or it was present before or at Visit 70 and increased in severity during the SFU. An AE that becomes serious during the SFU will also be considered as NEAE. If more than 1 AE is reported before or at Visit 70 and coded to the same preferred term, the AE with the greatest severity will be used as the benchmark for comparison with the AEs occurring during the SFU that were also coded to that preferred term.

An AE that occurs more than 30 days after the date of the last dose of IP will not be counted as an NEAE.

An SAE that occurred between the date of the first dose of IP in the OLTP and 30 days after the date of the last dose of IP, inclusive, will be considered a treatment-emergent SAE (e.g., TESAE).

The overall number and percentage of patients with TEAEs, NEAEs, death, TESAEs, TEAEs leading to study discontinuation and TEAEs related to study drug during the OLTP will be tabulated overall, and during the DBTP and the SFU by treatment group.

The incidence of common ( $\geq 2\%$  of patients in any treatment group) TEAEs and NEAEs during the OLTP will be summarized overall by preferred term. Similarly, the incidence of common TEAEs and NEAEs during the DBTP and during the SFU will be summarized by preferred term and treatment group and will be sorted by decreasing frequency starting with the weekly rapastinel group followed by the clinically driven schedule rapastinel group.

Listings will be presented for all patients with AEs and patients who died (if any).

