## **12.0 DETERMINATION OF SAMPLE SIZE**

The sample size and power calculations are based on the analysis of time to relapse during the first 52 weeks of the DBTP. Assuming a relapse rate of 19% per 26 weeks in the placebo group and a dropout rate of 20% per 26 weeks in all treatment groups, the sample size of 200 per group will have 90% power to detect a hazard ratio of 0.475 for a rapastinel treatment versus placebo at a 0.05 significance level. To achieve this number of randomized patients, approximately 1400 patients need to be enrolled in this study if 50% of patients are qualified for randomization.

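### Double-blind-period adverse events are shown by arm only as crude percentages, although the plan's own assumptions imply unequal time at risk; rates per time at risk should stand beside them

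*SAP*

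**What the plan says.** SAP 9.1 plans two kinds of DBTP adverse event output by arm. The overall table counts patients with TEAEs, NEAEs, TESAEs, deaths, discontinuations and related events, as numbers and percentages. The common-event table uses a threshold of 2% of patients in any group, and its contents "will be summarized by preferred term and treatment group and will be sorted by decreasing frequency starting with the weekly rapastinel group". That sentence concerns layout; the overall table and the threshold show that the measure is a proportion of patients. Protocol 9.7.6.1 uses the same measure. The visible AE text of either document has no person-time rate, time-to-first-event summary or cumulative incidence.

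Time in the DBTP depends on the efficacy outcome. Protocol 9.1.2 states: "Each randomized patient will be treated until relapse criteria are met", or until 52 weeks are completed or the patient leaves for another reason. SAP 2.0 ends the DBTP at the same points. Protocol 9.2 expects symptoms to return in patients switched to placebo. SAP 12.0 puts figures on this: "Assuming a relapse rate of 19% per 26 weeks in the placebo group", "a dropout rate of 20% per 26 weeks in all treatment groups", and a target hazard ratio of 0.475.

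SAP 7.1 does describe DBTP treatment duration and number of IV doses by treatment group, but nothing links these to the AE tables.

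**The concern.** A crude percentage is a fair basis for comparing arms when they are observed for similar lengths of time. Here relapse ends observation, and relapse is the outcome that treatment is meant to change. If rapastinel works as designed, its patients are watched for longer, and an AE that accrues steadily and is unrelated to treatment will be counted more often in the rapastinel arms. Tables set out by arm invite comparison even when no test is planned. The separate duration summary does not let a reader correct them, because time at risk for a given AE stops at its first occurrence.

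**Working it through.** **Inputs.** From SAP 12.0: placebo relapse 19% per 26 weeks, dropout 20% per 26 weeks in every arm, 200 patients per group, hazard ratio (HR) 0.475, level 0.05. Allocation is equal (SAP 2.0: "where patients are randomized 1:1:1 to either rapastinel 225 or 450 mg weekly", with the other two arms at the same ratio). Protocol 9.7.5 gives the sidedness: "All statistical tests will be 2-sided hypothesis tests performed at the 5% level of significance". The follow-up cap is 52 weeks. Exponential times are assumed throughout.

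**Weekly hazards**
- Placebo relapse: −ln(0.81)/26 = 0.008105
- Rapastinel relapse: 0.475 × 0.008105 = 0.003850
- Dropout: −ln(0.80)/26 = 0.008582
- Total exit: 0.016687 on placebo, 0.012432 on rapastinel

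**Reproducing the plan's figure.** The SAP states that "the sample size of 200 per group will have 90% power to detect a hazard ratio of 0.475". Expected relapses per arm are 200 × relapse/exit × (1 − exp(−52 × exit)):
- Placebo: 200 × 0.4857 × 0.5801 = 56.3
- Rapastinel: 200 × 0.3097 × 0.4761 = 29.5
- Total: 85.8

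Freedman's formula gives Φ(√85.8 × 0.525/1.475 − 1.960) = 90.9%. A Wald test on the log hazard ratio with variance 1/56.3 + 1/29.5 gives 90.6%. Schoenfeld's formula gives 93.2%, and a simulated log-rank test (20,000 runs) gives 92.2%. The stated 90% is reproduced closely enough to use the same inputs for exposure.

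**Mean time in the DBTP** = (1 − exp(−52 × exit))/exit:
- Placebo: 0.5801/0.016687 = 34.8 weeks (133.7 patient-years per 200 patients); 42.0% still on treatment at 52 weeks
- Rapastinel: 0.4761/0.012432 = 38.3 weeks (147.3 patient-years per 200 patients); 52.4% still on treatment at 52 weeks
- Ratio: 1.10

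**Crude AE percentage under an equal hazard.** The documents give no AE hazard. I assume it is constant and equal in both arms, at h per week. The crude risk is h/(h + exit) × (1 − exp(−52 × (h + exit))).

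| AE hazard per 100 patient-years | Placebo | Rapastinel | Ratio |
|---|---|---|---|
| 3.0 | 2.0% | 2.2% | 1.10 |
| 7.7 | 5.0% | 5.5% | 1.10 |
| 16.0 | 10.0% | 11.0% | 1.10 |
| 34.5 | 20.0% | 21.9% | 1.09 |
| 83.2 | 40.0% | 43.4% | 1.09 |

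**Rate with time at risk ending at first event or exit.** In the third row, h = 0.003078 per week.
- Placebo: mean time at risk 0.6422/0.019765 = 32.5 weeks; 0.1000/32.5 × 5200 = 16.0 per 100 patient-years
- Rapastinel: mean time at risk 0.5536/0.015510 = 35.7 weeks; 0.1099/35.7 × 5200 = 16.0 per 100 patient-years

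The ratio returns to 1.00. A 52-week time-to-first-event estimate that censors at exit would be 1 − exp(−0.160) = 14.8% in both arms.

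**Sensitivity of the exposure ratio**
- HR 0.3: 1.14; HR 0.7: 1.06; HR 1.0: 1.00; HR 1.3: 0.95
- Placebo relapse of 10% to 50% per 26 weeks, at HR 0.475: 1.05 to 1.32
- Adding 30 days (4.29 weeks) in both arms: (38.30 + 4.29)/(34.76 + 4.29) = 1.09

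**Early-onset AEs.** If the equal hazard is confined to the first 1 to 8 weeks, the crude ratio is only 1.002 to 1.017. For the first 2 to 8 weeks, dividing by whole-period person-time gives about 1.004/1.102 = 0.91 to 1.017/1.102 = 0.92. The rate then errs in the opposite direction.

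**The case against.** The strongest reply is that the tables are descriptive. The Protocol synopsis says so for all safety parameters, and no between-arm AE test or risk ratio is visible. The shift is also small against sampling noise at 200 per arm. For 10.0% v 11.0% it is 0.010/√(0.10×0.90/200 + 0.11×0.89/200) = 0.010/0.0307, or 0.33 standard errors. For 20.0% v 21.9% it is about 0.47. This stands, and it keeps the point minor. It does not remove it, because the cause is systematic and can be corrected with dates already collected.

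A reader might infer that the plan will inflate rapastinel's AE percentages. The documents do not support that. Shorter stay on placebo is the efficacy hypothesis and not a known fact, and the direction follows the hazard ratio. Nor would every treatment-unrelated AE appear more often on rapastinel. Early-onset AEs are barely affected, and AEs tied to returning depression could raise the placebo percentages. Relapse criteria include suicide risk and need for hospitalization, so exit and AEs are not independent; the documents give no figure for this.

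A reader might also infer that unequal exposure goes unreported. SAP 7.1 reports it; only the link to AE incidence is missing. Text not visible in the safety sections cannot be counted as absent.

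Two further points shape the remedy. A person-time rate has its own bias for early-onset AEs, so it cannot replace the percentage. Patients in the clinically driven arm receive placebo at visits judged stable, so their time in the DBTP is not time on rapastinel. Finally, SAP 15.0 limits output to an abbreviated report, which argues for a short addition.

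**Conclusion.** The point holds in conditional form, as a cheap improvement. The visible SAP 9.1 gives only crude DBTP percentages by arm, while the plan's own assumptions imply about 35 weeks at risk on placebo and 38 on rapastinel. For an AE with an equal and constant hazard, this produces a crude ratio of about 1.10, or 0.2 to 3.4 percentage points for placebo percentages of 2% to 40%. That size rests on exponential relapse and dropout, equal dropout in all arms, HR 0.475 in each rapastinel arm, and a constant AE hazard; the last is my assumption. The distortion is absent at HR 1, reverses above 1, grows with faster placebo relapse, and is negligible for AEs confined to the first weeks. It bears on how the safety tables are read and not on any planned test.

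**What to change.** In SAP 9.1, for the DBTP overall AE table, the common TEAE/NEAE table and the TESAE summary:

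- Beside each crude percentage, show the number of patients with the event per 100 patient-years at risk. End time at risk at the first event or at the end of the DBTP, so that numerator and denominator cover the same period. Handle the safety follow-up (SFU) separately, because SAP 9.1 tabulates it separately; running DBTP time on to 30 days after the last dose would mix the two.
- Keep the crude percentage, because the rate assumes a roughly constant hazard and can understate early-onset AEs in the longer-observed arm.
- For the overall TEAE/NEAE and TESAE rows, add a time-to-first-event cumulative incidence estimate by arm. State how exits are handled. Censoring at exit removes the exposure difference but assumes that exit is unrelated to the AE; counting relapse as a competing event would bring the difference back.
- Label the denominator of the clinically driven arm as time on assigned regimen, not rapastinel exposure.

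The cost is a few columns and one short summary, from dosing, AE and exit dates that the plan already uses. The downside is slightly longer descriptive tables in an abbreviated report. No planned output changes.

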# **11.0 INTERIM ANALYSIS**

No interim analysis is planned for this study.

## **12.0 DETERMINATION OF SAMPLE SIZE**

The sample size and power calculations are based on the analysis of time to relapse during the first 52 weeks of the DBTP. Assuming a relapse rate of 19% per 26 weeks in the placebo group and a dropout rate of 20% per 26 weeks in all treatment groups, the sample size of 200 per group will have 90% power to detect a hazard ratio of 0.475 for a rapastinel treatment versus placebo at a 0.05 significance level. To achieve this number of randomized patients, approximately 1400 patients need to be enrolled in this study if 50% of patients are qualified for randomization.

# **13.0** STATISTICAL SOFTWARE

Statistical analyses will be performed

#### 14.1 SUMMARY STATISTICS

The following statistical summaries will be presented for each type of data:

- Continuous variables will be summarized by descriptive statistics (number of patients, mean, standard deviation (SD), median, minimum, and maximum values).
- Categorical variables will be summarized by frequency distributions (counts and percentages).
- Time-to-event data will be summarized by showing the number of patients, number of patients experiencing the event of interest, estimates of the median, first quartile and third quartile using the Kaplan Meier estimate as well as a 95% CI for the median

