#### 8.0 EFFICACY ANALYSES

#### 8.1 PRIMARY EFFICACY PARAMETERS

The analysis of the primary efficacy parameter will be performed using the Double-blind mITT Population.

The primary efficacy parameter is the time to first relapse during the 52 weeks of the DBTP, defined as the number of days from the randomization date of DBTP to the relapse date (ie., relapse date – randomization date + 1). Relapse during the DBTP is defined as meeting any of the following criteria:

- Rater-administered MADRS total score  $\geq 18$  at 2 consecutive visits
- $\geq 2$  increase in CGI-S score compared with that obtained at randomization
- Risk of suicide as determined by the investigator
- Need for hospitalization due to worsening of depression as determined by the investigator
- Need for alternative treatment of depressive symptoms as determined by the investigator

Patients who did not meet the above relapse criteria during the 52 weeks of the DBTP, the time to relapse will be censored at the time of completion or discontinuation from the study, or 52 weeks, whichever is earlier.

The primary efficacy analysis will be presented by the cumulative distribution function of time to relapse characterized by the Kaplan-Meier curve for each treatment group.

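### Under the SAP's own planning rates, the Kaplan-Meier quantiles chosen to summarize time to relapse are almost all not estimable by Week 52, and no relapse proportion at a fixed week is planned

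*SAP*

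**What the plan says.** SAP 8.1 presents the primary analysis as the distribution of time to relapse, "characterized by the Kaplan-Meier curve for each treatment group". Patients who do not relapse are censored at completion, discontinuation or 52 weeks, whichever is earliest. SAP 15.0 lists this presentation as a major change from the protocol and limits output to what an abbreviated study report needs.

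The numbers that go with the curve come from the general conventions in SAP 14.1: patient and event counts, then "estimates of the median, first quartile and third quartile using the Kaplan Meier estimate as well as a 95% CI for the median". Time to relapse is the only time-to-event endpoint visible in the SAP.

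SAP 12.0 keeps the protocol's planning assumptions: "Assuming a relapse rate of 19% per 26 weeks in the placebo group", "a dropout rate of 20% per 26 weeks in all treatment groups", and "the sample size of 200 per group will have 90% power to detect a hazard ratio of 0.475".

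Protocol 9.7.5.1 also planned a log-rank test, a Cox hazard ratio with 95% interval and a Hochberg adjustment. The visible SAP text carries over none of these.

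**The concern.** A Kaplan-Meier median exists only if the curve falls to 50% during follow-up, and the other quantiles have the same kind of requirement. A relapse rate of 19% per 26 weeks does not bring any arm to 50% within 52 weeks.

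Since the SAP reduces the primary analysis to a curve, the section 14.1 estimates are the only tabulated Kaplan-Meier figures, and the median is the only quantity given an interval. If these cannot be estimated, the report shows a curve and counts but cannot state any arm's relapse risk with its uncertainty.

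**Working it through.** **Inputs.** From SAP 12.0: placebo relapse 19% per 26 weeks, dropout 20% per 26 weeks, hazard ratio 0.475, 200 per group, alpha 0.05. From Protocol 9.7.5: two-sided tests. From SAP 8.1: censoring at 52 weeks. Assumption: constant hazards, because the documents give only 26-week rates. The hazard ratio of 0.475 is applied to both rapastinel arms.

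**Reproducing the stated power.**
- Placebo relapse hazard: h = −ln(0.81)/26 = 0.00810 per week. Rapastinel: 0.475 × 0.00810 = 0.00385.
- Dropout hazard: d = −ln(0.80)/26 = 0.00858 per week.
- Expected events: 200 × h/(h+d) × (1 − exp(−52(h+d))) = 56.3 on placebo and 29.5 on rapastinel, 85.8 in total.
- Freedman power: Φ(√85.8 × 0.525/1.475 − 1.96) = 0.909. A 90% power needs 83 events, or 194 per group. The Schoenfeld form gives 0.932.

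The stated 90% with 200 per group is reproduced, so this reading of the assumptions is reasonable.

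**Quantiles.** The time to a relapse proportion q is −ln(1−q)/h.

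| | Placebo | Rapastinel |
|---|---|---|
| Relapse by Week 52 | 1 − 0.81² = 34.4% | 1 − 0.6561^0.475 = 18.1% |
| First quartile | Week 35.5 | Week 74.7 |
| Median | Week 85.5 | Week 180 |
| Third quartile | Week 171 | Week 360 |

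Only the placebo first quartile falls within 52 weeks. With four quantile items per arm (median, its interval, first and third quartile) and three arms, 11 of 12 are expected to be not estimable.

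**Sampling variation.** In 4,000 simulated trials with 200 per arm and the planned dropout:
- The median and third quartile were estimable in 0% of trials in either arm.
- The first quartile was estimable in 99.5% on placebo and 1.5% on rapastinel.
- A lower limit for the median (log-log) existed in 2.7% on placebo and 0% on rapastinel. An upper limit never existed.

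**Sensitivity.**
- Reading 0.19/26 as the weekly hazard gives 31.6% placebo relapse by Week 52 and a median at Week 94.9.
- Reading 19% and 20% as observed proportions with competing exits gives 38.2% and Week 74.8. The placebo median is then estimable in about 0.1% of trials, and its lower limit in about 20%.
- A placebo median at Week 52 needs 1 − √0.5 = 29.3% relapse per 26 weeks. If the first 26 weeks do show 19%, the second 26 would need 1 − 0.5/0.81 = 38.3%.
- A rapastinel arm reaches its first quartile by Week 52 only if its hazard ratio is at least ln(0.75)/(2 ln 0.81) = 0.683.

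**What fixed weeks would give.**
- Expected relapse at Week 26 is 19.0% on placebo and 1 − 0.81^0.475 = 9.5% on rapastinel.
- At Week 52 the Greenwood standard error is S(52) × √{[h/(200(h+d))] × [exp(52(h+d)) − 1]}, which gives 3.8 points on placebo and 3.1 on rapastinel. The 95% intervals are about ±7.4 and ±6.0 points.
- Expected numbers at risk at Week 52: 200 × 0.656 × 0.64 = 84 on placebo and 200 × 0.819 × 0.64 = 105 on rapastinel.

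**The case against.** Five points can be made for the plan.

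1. **Much of the output survives.** A reader might infer that nearly every planned number is lost. That is not so. The section 14.1 sentence also asks for patient and event counts. Across three arms these give 6 reportable items, and the placebo first quartile makes 7 of 18.

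2. **The curve adjusts for censoring.** A reader might infer that only crude relapse counts are left, distorted by 36% dropout. But the curve in SAP 8.1 is the censoring-adjusted estimate at every week. The 36% (1 − 0.80²) is net dropout. With relapse as a competing exit, dropout before relapse is d/(h+d) × (1 − exp(−52(h+d))), about 30% on placebo and 33% on rapastinel. What is missing is a tabulated value with its interval.

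3. **Section 14.1 is a general convention, and a median not reached is a legitimate finding.** This is true, but it says only that relapse stayed below 50%, which the design already assumes for every arm.

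4. **The missing comparison comes from SAP 15.0, not 14.1.** This stands. Dropping the test and the hazard ratio is a disclosed change of scope, and proportions by arm do not reverse it.

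5. **The precision assumes the full design.** This also stands. Shorter follow-up makes the quantiles less estimable, but it also weakens a Week 52 estimate. A fallback week without a stated threshold would let the time point be chosen after the data are seen.

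Parts of the SAP are withheld, so any statement about what is not planned applies to the visible text only. Section 8.1 appears intact.

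**Conclusion.** The point holds as a reporting weakness on the primary endpoint. Under the SAP's own rates, no arm is expected to yield a median, a third quartile or a usable interval for the median, and the first quartile appears on placebo only. No quantile can therefore be compared between placebo and rapastinel.

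The conclusion rests on roughly constant hazards, on a hazard ratio of 0.475 in both rapastinel arms and on 52 weeks of follow-up. It is stable across the readings of the 26-week rate tried above. It would change for placebo only if relapse ran near 29% per 26 weeks or rose sharply in the second half-year. A rapastinel arm with a hazard ratio of 0.683 or more would gain a first quartile but still no median.

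The documents do not support the inference that the endpoint goes unreported. The curve and the counts stand.

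**What to change.** In SAP 14.1 and 8.1, report for each arm the Kaplan-Meier cumulative relapse proportion at prespecified Weeks 26 and 52, with a 95% interval (log-log transform) and the number at risk. Keep the quartiles as supplementary output.

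If follow-up may be cut short, set a numeric minimum number at risk per arm before unblinding. Below that number the Week 52 estimate is not reported and Week 26 becomes the landmark.

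The cost is a sentence or two in the SAP, an option in the same Kaplan-Meier procedure and a little extra output. No new data are needed. Precision will be worse than shown above with fewer patients or shorter follow-up. The change gives each arm an estimate with its uncertainty; whether to reinstate the protocol's between-arm test is a separate decision.
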